Drug treatment pregnenolone or placebo will be initiated on a fixed titration schedule starting at 50 mg twice daily (100 mg/day) for one week, 150 mg in the morning and 150 mg in the evening (300 mg/day) for one week, and then 250 mg in the morning and 250 mg in the evening (500 mg/day). If clinically significant side effects are reported with either active medication or placebo, based on their clinical judgment the protocol psychiatrist may stop or delay titration or decrease dose, in a double-blinded fashion.

The 16-week, double-blind treatment will be divided into two stages of 8 weeks each. Stage 1 will be 8 weeks (baseline to Week 8) and Stage 2 will be 8 weeks (Week 8 to Week 16), for a total of 16 weeks. During the first stage of SPCD, the focus is on comparing pregnenolone and placebo treatment across all participants. The second stage re-randomizes placebo non-responders to pregnenolone and placebo, and as such focuses on comparing pregnenolone and placebo in placebo non-responders only.

During Stage 1, participants meeting all eligibility criteria will be randomized to receive placebo or pregnenolone in a 2:1 ratio. More participants receive placebo in Stage 1 so that there is a sufficient number of participants who receive placebo to be randomized again in the second phase.

For the second 8-week stage, placebo non-responders in phase one will be re-randomized to receive pregnenolone or placebo with a 1:1 ratio. Placebo non-responders are defined as having < 50% decrease in their MADRS score between Stage 1 baseline and Week 8. All other participants

STU102017-068, Brown, FormA-Protocol, Mod_33, 01-30-24 (8)

(Stage 1 participants on pregnenolone and placebo responders) will remain in the same group as assigned in the original randomization. A study psychiatrist and a research coordinator will reassess participants for 16 weeks (Baseline, Weeks 1, 2, 4, 8, 9, 10, 12, 16) on mood, neurocognitive, medication adherence, and safety measures. Weeks 6 and 14 will be done over the phone and will include MADRS only. Baseline, Week 8, and Week 16 visits will be done in-person. Virtual appointment options will be available for Week 1,2,4,9,10 visits. Vital signs and urine tests will not be collected for virtual appointments.

4. Study Procedures:

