Individuals who contact the research clinic (BL8.224 or the Simches Research Building at MGH) will first be screened over the phone (short 15-minute interview) to determine initial eligibility and will be asked questions about their demographic information, medical and psychiatric history, symptoms, medications, allergies, substance use and smoking history. Individuals who appear to meet initial eligibility after completing the phone screen will be invited to come to the clinic for an in-person eligibility assessment visit (Baseline, Visit 1). Participants who sign the informed consent, meet the inclusion criteria and do not meet any of the exclusion criteria at Baseline will be randomized into the study within 2 days of the Baseline visit using the randomization protocol described in section 3 (Concise Summary of Project). While eligibility as determined by mood assessments, cognitive tasks, and some safety assessments (i.e., Section 7, "Clinically significant laboratory, physical examination) will take between 24-48 hours to be assessed. Once this is complete, the subject will be randomized by the unblinded statistician at UTSW.

If the subject initially seems eligible we will distribute her study medication to her in the Baseline V1, but will instruct her not to use the medication until their eligibility has been officially determined and she receives notification from the study team. If the study medication cannot be distributed to the study subject at V1, it will be sent to her via overnight mail.

The study participation will last 16 weeks, with reassessments during 48-96 hours post baseline (via phone), Weeks 1, 2, 4, 6 (via phone), 8, 48-96 hours post baseline (via phone), 9, 10, 12, 14 (via phone), and 16 (See Assessment Schedule Table below). All visits can be scheduled \pm 2 business days of the timeline set on the assessment schedule. Participants will be paid \$100 at Baseline, Week 8, Week 16, at UTSW (\$50 at MGH), \$50 at Weeks 1, 2, 4, 9, 10, 12, and \$25 at phone calls on Weeks 6 and 14 (at UTSW only) with maximum compensation for the study being \$650 at UTSW and \$390 at MGH. DART transportation passes will also be provided to UTSW participants and parking vouchers for MGH participants.

	Visit 1	Visit 2	Visit 3	Visit 4	Visit 5	Visit 6	Visit 7	Visit 8	Visit 9	Visit 10	Visit 11	Visit 12	Visit 13

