The sample size calculation was performed using a customized program in SAS (v9.2), and was based on the SPCD sample size formula that takes into account the mean treatment effect

combined with equal weighting of each stage-wise estimate and its variance, and subject retention rates for the trial. We assume 67% placebo non-responders in Stage 1, 10% dropout rate for Stage 1 and 5% dropout in Stage 2. The sample size calculation was performed for a continuous response assuming a Stage 1 mean change from baseline to Week 8 in total MADRS score between pregnenolone and placebo of 3.5 (standard deviation (SD) of 8) and a Stage 2 difference of 5 (SD=8). Given these assumptions, a sample size of 144 subjects (randomized in 2:1 ratio at Stage 1 for placebo and pregnenolone) will have 90% power to detect a change from baseline in total MADRS score between pregnenolone and placebo. This assumes a two-sided hypothesis test with 0.05 significance is used for the comparison between pregnenolone and placebo.

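### The plan names no covariate or model for the primary MADRS comparison; prespecifying baseline adjustment in each stage would be a small, low-cost improvement, not a correction of an error.

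*Combined protocol and SAP*

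**What the plan says.** Section 15 (Power Analysis & Sample Size Determination) describes the comparison through its sample-size formula. The mean treatment effect is "combined with equal weighting of each stage-wise estimate and its variance". The inputs are a Stage 1 difference in MADRS change of 3.5 with SD 8 "and a Stage 2 difference of 5 (SD=8"), tested two-sided at 0.05. On attrition: "We assume 67% placebo non-responders in Stage 1, 10% dropout rate for Stage 1 and 5% dropout in Stage 2". The conclusion is that 144 women, randomized 2:1 to placebo in Stage 1, "will have 90% power to detect a change from baseline in total MADRS score between pregnenolone and placebo".

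No section names a covariate, an analysis of covariance or a mixed model.

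Section 3 defines who enters the Stage 2 comparison: "Placebo non-responders are defined as having < 50% decrease in their MADRS score between Stage 1 baseline and Week 8". It sets the periods as "Stage 1 will be 8 weeks (baseline to Week 8) and Stage 2 will be 8 weeks (Week 8 to Week 16"). Section 4 makes MADRS the primary outcome measure and schedules it at every visit, including the phone contacts, so both stage-start values are collected.

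**The concern.** Read alone, Section 15 permits an unadjusted comparison of change scores. A change score fixes the slope of the final value on the starting value at 1. When the true slope is lower, as it usually is for a rating scale, adjusting for the starting value gives a smaller variance.

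This matters most in Stage 2, which has about 27.5 women per arm and contributes 68% of the variance of the combined estimate. The Week 0 score precedes the first randomization. The Week 8 score determines entry to the second and so precedes it. Each is therefore a valid covariate for its stage.

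Prespecification is the second reason. Section 15 does not say what Stage 2 change is measured from. Change from Week 0, change from Week 8 and a baseline-adjusted analysis would all fit the text. Because placebo non-responders are re-randomized, all three target the same expected treatment difference in Stage 2, but they would report different numbers with different precision. The choice should be made before anyone can see the results.

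**Working it through.** **1. The plan's own figure.** All inputs are from Sections 3 and 15.

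- Stage 1 completers: placebo 96 × 0.9 = 86.4; pregnenolone 48 × 0.9 = 43.2.
- Stage 2 per arm: 86.4 × 0.67 × 0.95 / 2 = 27.5.
- V1 = 64 × (1/86.4 + 1/43.2) = 2.222, so SE1 = 1.491.
- V2 = 64 × 2/27.5 = 4.655, so SE2 = 2.158.
- Stage 2 share of variance: 4.655 / (2.222 + 4.655) = 0.677.
- Combined effect: 0.5 × 3.5 + 0.5 × 5 = 4.25.
- Combined SE, taking the stage estimates as uncorrelated: 0.5 × √(2.222 + 4.655) = 1.311.
- Power = Φ(4.25/1.311 − 1.960) = 90.0%.

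The stated 90% reproduces.

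**2. Cost of the covariates.** Estimating q slopes inflates a stage's variance by about 1 + q/(N − q − 3), with N = 129.6 in Stage 1 and 55 in Stage 2.

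- One covariate per stage: factors 1.008 and 1.020, SE 1.322, power 89.5%.
- With site as a second covariate: factors 1.016 and 1.040, SE 1.332, power 89.1%.

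These are the worst cases, in which adjustment gains nothing over the change score.

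**3. Possible gain.** The documents give no correlations, SD ratios or mean MADRS, so everything in this step is assumed. Eight trivariate normal sets were used, with Week 0 mean 28 and the Week 8 mean set so that 67% have a decrease below 50%. Stage 2 was restricted to those women. The comparator is change from Week 0 in Stage 1 and from Week 8 in Stage 2.

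The Stage 1 ratio of adjusted to change-score variance is s8²(1 − r²) / (s0² + s8² − 2·r·s0·s8). For set 1 it is 64 × 0.8775 / (25 + 64 − 28) = 0.921. The Stage 2 ratio comes from simulating the selected women.

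Power uses SE = 0.5 × √(V1 × ratio1 × 1.008 + V2 × ratio2 × 1.020). For set 1 this is 0.5 × √(2.063 + 4.169) = 1.248, and power is Φ(4.25/1.248 − 1.960) = 92.6%.

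| Set | SD at Weeks 0/8/16 | r(0,8), r(8,16), r(0,16) | Stage 1 ratio | Stage 2 ratio | Power, stage-start MADRS only |
|---|---|---|---|---|---|
| 1 | 5/8/8.5 | .35, .45, .25 | .921 | .878 | 92.6% |
| 2 | 5/8/8.5 | .35, .60, .25 | .921 | .920 | 91.8% |
| 3 | 5/8/8.5 | .35, .75, .30 | .921 | .963 | 91.0% |
| 4 | 7/8/8 | .50, .45, .40 | .842 | .860 | 93.6% |
| 5 | 7/8/8 | .50, .60, .40 | .842 | .898 | 92.9% |
| 6 | 7/8/8 | .50, .75, .45 | .842 | .942 | 92.1% |
| 7 | 5/8/8 | .50, .40, .45 | .980 | .859 | 92.4% |
| 8 | 5/8/8.5 | .35, .40, .35 | .921 | .878 | 92.6% |

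The SE runs from 1.221 to 1.288. In sample-size terms that is 144 × (1.311/1.288)² = 149 to 144 × (1.311/1.221)² = 166. With site added and its cost charged, power is 90.5 to 93.2%.

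**4. Meaning of SD 8.** Section 15 does not say whether SD 8 is a raw change SD or a baseline-adjusted residual SD. If it is residual, the adjusted analysis has 89.5% power (89.1% with site). An unadjusted change from Week 0 in Stage 1 and from Week 8 in Stage 2 would then have 85.0 to 88.4% in the same sets.

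**The case against.** Several objections stand, and they limit the claim.

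- Section 15 is a sample-size section. Planning on a plain change SD is common and often conservative. A reader might infer that the trial is committed to an unadjusted test; the documents do not say so. They are silent on covariates, and the wider gap is that they give no primary analysis model.
- No gain can be shown from the documents. Every correlation and SD ratio in step 3 is assumed.
- The assumed sets do not all match SD 8. Their Stage 1 change SDs are 7.0 to 7.8. Their Stage 2 change SDs among non-responders run from 5.4 to 8.3, with sets 3 and 6 furthest from the plan (5.7 and 5.4). Only the variance ratios were carried over to SD 8, so the table gives formula values, not simulated power. Simulating the sets at their own SDs with effects of 3.5 and 5 (4,000 trials each) gave gains of only 0.2 to 2.9 points over the change score.
- Section 4 lists a contact after Week 8 as post-baseline ("8, 48-96 hours post baseline (via phone), 9, 10, 12, 14 (via phone), and 16"), but Table 1 calls it post Week 8, so this may be a copying slip. It is weak evidence that Week 8 is the Stage 2 baseline. The Week 8 to Week 16 definition in Section 3 is better evidence.
- The documents do not say that randomization is stratified by site, so there is no firm case for adjusting for it.

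These points reduce the size and certainty of the benefit. They do not remove the case for naming one adjusted analysis in advance, because the data are already collected and the possible loss is small.

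**Conclusion.** This is a worthwhile improvement and not an error. The 90% power at 144 women is correct for an equally weighted comparison with SD 8.

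Under the assumed sets, adjusting for stage-start MADRS alone gives about 91 to 94% by formula. The worst case is 89.5%, or 89.1% if site is added. If SD 8 is already a residual SD there is no gain over the planned figure, and adjustment would instead protect it.

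Two stronger readings should be resisted. One is that the trial is underpowered. The 85.0 to 88.4% figures apply only if SD 8 is residual and the analysis is then left unadjusted, and the documents establish neither. The other is that adjustment would raise power well above 94% or justify a smaller trial. That needs assumptions such as equal SDs before and after treatment, or Stage 2 change measured from Week 0, which the documents do not support.

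Confidence is medium: the validity of the adjustment is firm, its size is not.

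**What to change.** Before unblinding, add a paragraph that specifies a single primary analysis:

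- Stage 1: Week 8 MADRS on treatment and Week 0 MADRS.
- Stage 2, re-randomized placebo non-responders only: Week 16 MADRS on treatment and Week 8 MADRS, with Week 8 named as the Stage 2 baseline.
- Combine the two adjusted treatment estimates with the stated equal weights, and name the reference distribution for the test.
- Add site only if randomization is stratified by it, and say whether it is.
- A repeated-measures model could use the interim MADRS visits, including the phone assessments ("Weeks 6 and 14 will be done over the phone and will include MADRS only"), and the data of women who miss Week 8 or Week 16. List it as a named sensitivity analysis, not as an alternative primary.
- State in Section 15 whether SD 8 is a raw change SD or a residual SD, and keep 90% as the planning figure.

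The cost is the text and one degree of freedom per stage: at worst 0.5 power points, or 0.9 with site. No data, visits or patients are added.
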